8.1.1 Severity of Alopecia Tool (SALT)

The SALT is a measure of hair absence that quantifies the amount of scalp surface without hair in a pre-specified quadrant of the scalp (right side, top, left side, back), that is further summed after applying a quadrant-specific multiplier indicative of scalp surface area contribution, to provide an overall score of total hair loss. Total SALT score is computed as [(left quadrant raw score x 0.18) + (right quadrant raw score x 0.18) + (top quadrant raw score x 0.40) + (back quadrant raw score x 0.24)]. The SALT assessment will occur via live examination of the patient during clinic visits.

As the SALT score is by nature a measurement of total surface without hair, it is important to note that in the context of this SAP, endpoints will follow these definitions:

- Absolute change = difference in SALT measurements (follow-up SALT score minus baseline SALT score)
- Relative change = percent change of the follow-up SALT score, where baseline SALT score is the denominator (i.e. absolute change divided by the baseline score, multiplied by 100)

8.2 Exploratory Efficacy Endpoints

Exploratory efficacy endpoints include:

- The proportion of responders at Weeks 4, 8, 12, 16 and 20;
- Proportion of responders who have at least 75%, 90% and 100% relative reduction in SALT score from baseline at Weeks 4, 8, 12, 16, 20, and 24;
- Absolute change in SALT scores from baseline at Weeks 4, 8, 12, 16, 20, and 24 in the Blinded Treatment Period;
- Relative change in SALT scores from baseline at Weeks 4, 8, 12, 16, 20, and 24 in the Blinded Treatment Period;
- Absolute SALT scores at Weeks 4, 8, 12, 16, 20, and 24 in the Blinded Treatment Period;
- Proportion of patients achieving an absolute SALT score of ≤ 10 , ≤ 20 , and ≤ 25 at Weeks 4, 8, 12, 16, 20 and 24;
- Percent change in alopecia areata severity from baseline as measured by the clinician VAS-S at Weeks 12 and 24;

- Changes in alopecia areata from baseline as measured by the clinician rated 7-point Likert scale CGI-I at Weeks 12 and 24;
- Proportion of subjects worsening in alopecia areata from baseline to Weeks 12 and 24 as measured by responses of “Very Much Worse” or “Much Worse” on the clinician rated CGI-I;
- Proportion of subjects improving from baseline to Weeks 12 and 24 as measured by responses of “Very Much Improved” or “Much Improved” on the clinician rated CGI-I;
- Percent change in alopecia areata severity from baseline as measured by the patient VAS-S at Weeks 12 and 24;
- Changes in alopecia areata from baseline as measured by the patient rated 7-point Likert scale PGI-I at Weeks 12 and 24;
- Proportion of subjects worsening in alopecia areata from baseline to Weeks 12 and 24 as measured by responses of “Very Much Worse” or “Much Worse” on the patient rated PGI-I;
- Proportion of subjects improving from baseline to Weeks 12 and 24 as measured by responses of “Very Much Improved” or “Much Improved” on the patient rated PGI-I;
- Patient-reported outcomes: Changes in symptoms from baseline as measured by AASIS and exploratory questions at Week 24.

8.2.1 Visual Analog Scale (VAS)

The VAS is a scale initially developed for pain that has been used in a variety of clinical settings where the endpoint of interest is based on patient perception. The VAS is a distinct 100 millimeter line anchored on the left end at full degree of impairment and on the right end at no degree of impairment, where indication of the degree of impairment perceived at the time of assessment is captured by marking the appropriate position on the line between the anchor points. The measured distance of the mark from the left anchor will be recorded in millimeters. Since the VAS was measured right to left in terms on increasing impairment, the VAS analysis value will be calculated by taking 100 minus the collected value.

Clinician VAS of Severity (VAS-S)

The Investigator will complete a VAS-S regarding the severity of the patient’s alopecia areata at the time of completion as indicated in the Schedule of Events. The left and right anchor points for the clinician VAS-S are “Extremely Apparent” and “Not At All Apparent”, respectively.

Patient VAS of Severity (VAS-S)

Patients will rate perception of his/her alopecia areata severity on the patient VAS-S. The left and right anchor points for the patient’s alopecia areata VAS-S are “Extremely Apparent” and

“Not At All Apparent”, respectively. The patient VAS-S will measure the patient’s perception of his/her alopecia areata at the time of completion.

8.2.2 Clinical Global Impression of Improvement (CGI-I)

Compared to the patient’s alopecia areata prior to treatment at baseline, the patient’s current state of alopecia areata will be assessed according to the Investigator’s perceived change. The Investigator may select one of seven numeric choices from 1 to 7, with 1 representing “Very Much Improved” to 7 representing “Very Much Worse”.

8.2.3 Patient Global Impression of Improvement (PGI-I)

Compared to the patient’s alopecia areata prior to treatment at baseline, the patient’s current state of alopecia areata will be assessed according to his/her perceived change. The patient may select one of seven numeric choices from 1 to 7, with 1 representing “Very Much Improved” to 7 representing “Very Much Worse”.

8.2.4 Patient Reported Outcomes: Alopecia Areata Symptom Impact Scale (AASIS) and Exploratory Questions

The AASIS is a questionnaire designed to measure the quality of life, symptoms, and their impact for patients with alopecia areata [[Mendoza 2013](#)]. Three dimensions related to alopecia areata are assessed: impact of alopecia areata, hair loss, and physical skin symptoms. All responses will be summed to produce the AASIS score.

In addition to the AASIS, exploratory questions will be used to attempt to define clinically meaningful outcomes for patients with alopecia areata.

8.3 Overview of Efficacy Analysis Issues

8.3.1 Handling of Dropouts or Missing Data

The Last Observation Carried Forward (LOCF) approach will be implemented for missing SALT score data, e.g., if the SALT score in the Week 16 visit window is missing, the next and closest available on-treatment SALT score measurement before the Week 16 visit window will be used for all remaining SALT assessments: Week 16, Week 20 and Week 24. Missing baseline values will not be carried forward. If a SALT assessment is missing between two non-missing SALT

assessments visits, the SALT score at that visit will be interpolated using the mean of the closest pre- and post-assessments.

If the number of discontinuations due to adverse events is substantial, other methods will be explored.

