8.4 Analysis Methods

All statistical tests will be 2-sided with a significance value of 0.05. Testing will be based on the Efficacy population and performed only for the Treatment Period. An analysis of the primary efficacy endpoint and exploratory SALT endpoints will also be performed for the Per Protocol population. The final efficacy analysis will be conducted when all patients in the 12 mg cohort have completed Week 24. The placebo groups from all 3 cohorts will be pooled and compared to each active dose (4 mg, 8 mg, and 12 mg) individually. Active doses, 4 mg, 8 mg, and 12 mg, will also be compared. There will be no adjustment for multiple treatment group comparisons in this dose-ranging Phase 2 study.

Table 8-1 gives an overview of the analysis methods that will be used for each of the efficacy variables.

Table 8-1 Efficacy Variables and Analysis Methods

Efficacy Variables	Collection Times	Method
Primary		
Responder Analysis SALT (50% relative reduction)	Baseline, Week 24	χ^2 Test
Exploratory		
Responder Analysis SALT (50% relative reduction)	Baseline, Week 4, 8, 12, 16, 20	χ^2 Test
Responder Analysis SALT (75%, 90%, and 100% relative reduction)	Baseline, Week 4, 8, 12, 16, 20, 24	χ^2 Test
SALT (≤ 10 , ≤ 20 , ≤ 25 absolute score)	Baseline, Week 4, 8, 12, 16, 20, 24	χ^2 Test
SALT (absolute change)	Baseline, Week 4, 8, 12, 16, 20, 24	MMRM
SALT (relative change)	Baseline, Week 4, 8, 12, 16, 20, 24	MMRM
SALT (absolute score)	Baseline, Week 4, 8, 12, 16, 20, 24	MMRM
Clinician VAS-S (percent change)	Baseline, Week 12, 24	ANCOVA
Patient VAS-S (percent change)	Baseline, Week 12, 24	ANCOVA
CGI-I	Week 12, 24	χ^2 Test
CGI-I Responder (“Very Much/Much Improved” and “Much/Very Much Worse”)	Week 12, 24	χ^2 Test
PGI-I	Week 12, 24	χ^2 Test
PGI-I Responder (“Very Much/Much Improved” and “Much/Very Much Worse”)	Week 12, 24	χ^2 Test
AASIS	Baseline, Week 24	Descriptive Statistics
Exploratory Questions	Baseline, Week 24	Descriptive Statistics
Responder Analysis, Exploratory Questions, Satisfied v. Unsatisfied	Baseline, Week 24	χ^2 Test

χ^2 = Chi-Squared Test; ANCOVA = analysis of covariance; CMH = Cochran-Mantel-Haenszel; MMRM = mixed-effect model for repeated measures

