8.4.2 Exploratory Efficacy Analyses

Treatment differences for absolute score, absolute change, and relative change in SALT score from baseline to Weeks 4, 8, 12, 16, 20, and 24 will be assessed with a mixed-effect model of repeated measures (MMRM). The model will include fixed factors for treatment group, study visit, treatment by study visit interaction, and alopecia areata subtype, with baseline SALT score as a covariate. An unstructured variance-covariance matrix will be used. If convergence is not achieved, an alternative autoregressive covariance structure will be used. If the MMRM model does not converge, other covariance structures will be explored. If convergence is still not met, only descriptive statistics will be presented.

Point estimates and standard errors will be presented for each treatment group at each time point. P-values for the treatment by visit interaction will be presented at Week 24 for each active treatment compared to the placebo. A comparison of the active doses (4 mg vs. 8 mg, 4 mg vs. 12 mg, 8 mg v. 12 mg) will be presented as well. Treatments will be compared overall and by visit.

Descriptive statistics will be reported for the SALT score at each time point for each treatment group and by subtype. By-patient data listing will also be presented for patient SALT scores and collection of SALT photographs. The mean of observed value, absolute change, and relative change SALT scores along with standard errors for each treatment group will be presented using line graphs.

Responders, as defined for the primary endpoint, will be analyzed per section 8.4.1 for Weeks 4, 8, 12, 16, and 20. Additionally, the following responder groups will be analyzed per section 8.4.1 at Weeks 4, 8, 12, 16, 20, and 24: 1) patients who meet at least 75%, 90%, and 100% relative change; 2) patients who meet an absolute SALT score of ≤ 10 , ≤ 20 , or ≤ 25 .

The percent change in clinician and patient VAS-S from baseline will be assessed using the analysis of covariance (ANCOVA) for Week 12 and 24 with fixed factors for treatment, alopecia areata subtype, and baseline VAS-S. The least squares mean score estimates with 95% CI will be presented along with p-values for each treatment comparison at each time point. Descriptive statistics will also be reported by treatment and subtype.

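### SAP 8.3.1 fills missing SALT scores without exempting the MMRM, leaves open whether an early-termination SALT counts as Week 24, and names no missing-data sensitivity analysis

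*SAP*

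**What the plan says.** The protocol (12.4.2) leaves missing data to the SAP. SAP 8.3.1 states: "The Last Observation Carried Forward (LOCF) approach will be implemented for missing SALT score data". In its Week 16 example, the closest earlier "on-treatment SALT score measurement before the Week 16 visit window will be used for all remaining SALT assessments", through Week 24. For a gap between two attended visits, "the SALT score at that visit will be interpolated using the mean of the closest pre- and post-assessments". The only exemption is that missing baseline values are not carried forward. The only fallback is: "If the number of discontinuations due to adverse events is substantial, other methods will be explored".

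SAP 8.4.2 says that absolute score, absolute change and relative change in SALT "will be assessed with a mixed-effect model of repeated measures (MMRM"). It does not say whether observed or filled scores are used. SAP 12 records one change to the MMRM, the subtype term, and nothing on missing data. Dose comparisons are planned in 8.4 ("Active doses, 4 mg, 8 mg, and 12 mg, will also be compared") and again for the MMRM in 8.4.2. A second analysis set is also planned: "An analysis of the primary efficacy endpoint and exploratory SALT endpoints will also be performed for the Per Protocol population". SAP 4.4 makes a Week 24 SALT one of the conditions for that population.

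On early termination, protocol 8.3.1 has the Week 24 assessments done at that visit. Footnote 11 of the schedule of events makes the Week 24 visit double as the early-termination visit. SAP 8.3.3 keeps scheduled visits at their nominal label and does not move them by date.

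**The concern.** There are three gaps.

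1. **MMRM input.** An MMRM is used because it is valid under missing-at-random on the observed scores, without imputation. Carrying scores forward first discards that property. If hair is still regrowing at dropout, it pulls the Week 24 estimate towards an earlier, smaller effect. If dropout differs between doses, equally effective doses can look different.

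2. **Early-termination SALT.** Two sets of provisions can apply to the same patient, and no sentence says which governs. This reaches the primary endpoint as well as the exploratory analyses.

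3. **Sensitivity.** The fallback names no method and no threshold, and only adverse-event discontinuations trigger it. The Per Protocol repeat also excludes patients for dosing and deviations, so it is only a partial check on missing data in the Efficacy Population.

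**Working it through.** **Plan's own figures.** SAP 2.6: 28 v 28, 45% v 10%, two-sided 0.05, power above 80%. This reproduces: 85.5% by the normal approximation, 86.9% by exact enumeration of the chi-squared test. About 150 randomised and 120 completing gives 30/150 = 20% non-completion, so roughly 30 patients could have filled scores.

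**Early termination, one patient (illustrative scores).** Baseline 80, Week 8 = 60, drug stopped, off-drug early-termination SALT = 40 in Week 11.
- Footnote 11 with SAP 8.3.3: the 40 is the nominal Week 24 score. Reduction (80 - 40)/80 = 50%: responder. Weeks 12 to 20 now lie between two attended visits and are interpolated to (60 + 40)/2 = 50. The score also meets the Week 24 condition for Per Protocol.
- SAP 8.3.1: the on-treatment 60 is carried to Week 24. Reduction (80 - 60)/80 = 25%: non-responder.
- With Week 8 = 40 and early termination = 60, the answers swap.
- If the early-termination score was on treatment, LOCF can carry it and Week 24 agrees on both readings. Only the intermediate visits and the Per Protocol condition then differ. SAP 8.3.1 does not define *on-treatment* for SALT.

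**Effect on the Week 24 mean difference.** The documents give no SALT SD, regrowth curve or dropout by arm. Assumed: true relative change -50 active and -8 placebo (difference -42), dropout d = 20% in both arms and unrelated to outcome, last visit equally likely at Weeks 4, 8, 12, 16 and 20, early-termination scores **not** labelled Week 24. With f the mean share of the Week 24 effect reached at the last visit:

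filled difference = -42 × (1 - d(1 - f))

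| Curve | Shares at Weeks 4 to 20 | f | Filled difference |
|---|---|---|---|
| Flat to Week 8, then linear | 0, 0, 0.25, 0.5, 0.75 | 0.30 | -36.1 |
| Linear | 1/6, 1/3, 1/2, 2/3, 5/6 | 0.50 | -37.8 |
| Plateau from Week 16 | 0.25, 0.5, 0.75, 1, 1 | 0.70 | -39.5 |
| Early peak, later loss | 0.5, 1.0, 1.3, 1.3, 1.15 | 1.05 | -42.4 |

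In simulation (2,000 trials per scenario, first three curves, three SD sets), maximum likelihood on observed scores gave -41.9 to -42.3, with a standard error 2% to 12% larger.

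**If early-termination scores are labelled Week 24.** Assume all dropouts attend, at times uniform over Weeks 4 to 24, with linear regrowth. Mean share = 14/24 = 0.583, so even a model on observed scores gives -42 × (1 - 0.2 × 0.417) = -38.5.

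**Two equally effective doses.** False gap = 50 × (d1 - d2) × (1 - f). At an assumed 25% v 15% dropout: 50 × 0.10 × 0.5 = 2.5 points (1.5 to 3.5 over the first three curves). With 36 per arm and assumed SDs from √(25² + 8²) = 26.2 to √(40² + 12²) = 41.8, the standard error is SD × √(2/36) = 6.2 to 9.8. The 2.5-point gap is therefore about 0.25 to 0.40 standard errors.

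**Responders, LOCF against non-responder imputation (NRI).** Take 45% v 10% with full follow-up and 20% dropout in each arm. NRI gives 0.8 × 45 = 36% v 0.8 × 10 = 8%, a difference of 28.0 points. LOCF, with normally distributed relative change, the first three curves and three assumed SD sets, gives 29.0 to 32.3. For arm sizes, three equal active arms of n and pooled placebo of n/2 + n/2 + n/5 = 1.2n give 4.2n = 150, or about 36 v 43. Exact power there is 0.887 for NRI and 0.90 to 0.94 for LOCF. At 35 v 35, NRI power is 0.84.

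**The case against.** **The MMRM input is inferred from silence.** SAP 8.4.2 never says that filled scores are used, and the table shells are not available. A reader might conclude that the SAP prescribes an imputed MMRM; it does not say so. What stands is that an unrestricted rule with no exemption most naturally reaches the MMRM, and one sentence would settle it.

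**Early termination is a gap, not a contradiction.** The Week 16 case is only an example. If the early-termination score is held as Week 24, nothing is missing there. The worked patient also needs a 20-point change in about three weeks. All fair, but protocol 8.3.1 foresees patients who stop dosing before the visit, and neither reading is ruled out.

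**The dose distortion is small.** A reader might infer that LOCF would mislead dose selection. The documents do not support that: they give no dropout by dose, the gap is under half a standard error at the assumed split, and the dose comparisons are exploratory and run across sequential cohorts, which no missing-data method cures.

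**The simulation favours the observed-score model.** Dropout was random and interpolation was not simulated. This stands, so the figures show direction and order of size only.

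**NRI is a preference.** Its difference from LOCF is only 1.0 to 4.3 points, and a Per Protocol repeat is planned. NRI is one suitable choice among several; the point is that some method be named in advance.

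**Conclusion.** The point holds as three omissions in the SAP: no statement of which scores the MMRM uses, no rule for early-termination SALT, and no named missing-data sensitivity analysis of the Efficacy Population. The second matters most, because it can change primary responder status and because fitting the MMRM to observed scores does not remove the shrinkage until it is settled.

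At 20% dropout in each arm, and if early-termination scores are not labelled Week 24, the shrinkage is 2.5 to 5.9 points on an assumed -42. It can vanish if response reverses before Week 24, which is plausible in a disease that protocol 4.1 describes as cyclical. The placebo comparison is not threatened and the stated sample size is unaffected. The dose-comparison effect is a secondary concern. All sizes rest on the assumed means, curves, SDs and dropout pattern. The changes are worth making because they are cheap and reduce bias.

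**What to change.** 1. **Settle early termination first.** Reconcile SAP 8.3.1, 8.3.3 and footnote 11.
   - Count an early-termination SALT as Week 24, for the primary endpoint and the Per Protocol condition, only if it falls in the Week 24 window (±3 days).
   - Define *on-treatment* for SALT.
   - Keep an on-treatment score outside that window as the most recent score available to LOCF. For by-visit analyses assign it by a stated rule, for example to the next scheduled SALT visit not attended, but never to Week 24 unless in window.
   - Do not discard it because the nearest visit already has a score. A nearest-visit rule that only lists such scores would lose about 61% of them (timing uniform over Days 30 to 164 and all earlier visits attended, both assumed).
   - List and flag off-treatment early-termination scores, and keep them out of LOCF and the on-treatment MMRM.
   - Leave completers' Week 24 visits nominal.
2. **MMRM.** Fit it to observed on-treatment SALT scores only, without LOCF or interpolation, and state the missing-at-random assumption.
3. **Responders.** Keep LOCF as the primary rule. Replace the open-ended fallback with a named sensitivity analysis, such as NRI in the Efficacy Population, reported whatever the reason for discontinuation, and add its table to SAP 14.

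**Cost.** SAP wording, a little programming and one or two tables; no extra patients or data. The MMRM standard error rises slightly. The NRI result will look less favourable: 36% v 8% at 20% dropout, with power about 0.89 at 36 v 43 or 0.84 at 35 v 35.

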8.3.2 Multicenter Studies

Patients will be enrolled at up to 15 sites. To reduce variability, one rater should perform each clinician dependent assessment (SALT, VAS-S, and CGI-I) for the patient for the duration of the study. All investigators using the SALT will be trained prior to use.

8.3.3 Assessment Visit Windows

The visit schedule for all study assessments is provided in appendix 17.2. Patients will be considered completed for efficacy analyses after Week 24 (Visit 10). For Cohorts 1 and 2, patients will stop taking study medication upon completion of treatment at Week 24 and enter a 4-week Post-Treatment Safety Follow-Up Period. For Cohort 3, patients will either complete treatment at Week 24 and have a Safety Follow-up visit at Week 28 prior to exiting the study, or if eligible, may enroll into an Open-label Extension study of CTP-543 at their Week 24 visit.

For scheduled visits, there will be no reassignment of the analysis visit based on date, and all data will appear in summary tables based on the nominal timepoint.

Unscheduled and repeat safety visits will be assigned to the closest prior planned visit. If the closest planned visit is already documented, the unscheduled or repeat visit will only be listed and will not be summarized.

8.4 Analysis Methods

All statistical tests will be 2-sided with a significance value of 0.05. Testing will be based on the Efficacy population and performed only for the Treatment Period. An analysis of the primary efficacy endpoint and exploratory SALT endpoints will also be performed for the Per Protocol population. The final efficacy analysis will be conducted when all patients in the 12 mg cohort have completed Week 24. The placebo groups from all 3 cohorts will be pooled and compared to each active dose (4 mg, 8 mg, and 12 mg) individually. Active doses, 4 mg, 8 mg, and 12 mg, will also be compared. There will be no adjustment for multiple treatment group comparisons in this dose-ranging Phase 2 study.

Table 8-1 gives an overview of the analysis methods that will be used for each of the efficacy variables.

Table 8-1 Efficacy Variables and Analysis Methods

Efficacy Variables	Collection Times	Method
Primary		
Responder Analysis SALT (50% relative reduction)	Baseline, Week 24	χ^2 Test
Exploratory		
Responder Analysis SALT (50% relative reduction)	Baseline, Week 4, 8, 12, 16, 20	χ^2 Test
Responder Analysis SALT (75%, 90%, and 100% relative reduction)	Baseline, Week 4, 8, 12, 16, 20, 24	χ^2 Test
SALT (≤ 10 , ≤ 20 , ≤ 25 absolute score)	Baseline, Week 4, 8, 12, 16, 20, 24	χ^2 Test
SALT (absolute change)	Baseline, Week 4, 8, 12, 16, 20, 24	MMRM
SALT (relative change)	Baseline, Week 4, 8, 12, 16, 20, 24	MMRM
SALT (absolute score)	Baseline, Week 4, 8, 12, 16, 20, 24	MMRM
Clinician VAS-S (percent change)	Baseline, Week 12, 24	ANCOVA
Patient VAS-S (percent change)	Baseline, Week 12, 24	ANCOVA
CGI-I	Week 12, 24	χ^2 Test
CGI-I Responder (“Very Much/Much Improved” and “Much/Very Much Worse”)	Week 12, 24	χ^2 Test
PGI-I	Week 12, 24	χ^2 Test
PGI-I Responder (“Very Much/Much Improved” and “Much/Very Much Worse”)	Week 12, 24	χ^2 Test
AASIS	Baseline, Week 24	Descriptive Statistics
Exploratory Questions	Baseline, Week 24	Descriptive Statistics
Responder Analysis, Exploratory Questions, Satisfied v. Unsatisfied	Baseline, Week 24	χ^2 Test

χ^2 = Chi-Squared Test; ANCOVA = analysis of covariance; CMH = Cochran-Mantel-Haenszel; MMRM = mixed-effect model for repeated measures

